Secondarily to investigate whether treatment with *Lactobacillus rhamnosus* and *Lactobacillus reuteri* has a preventive effect on rUTI in postmenopausal women. In addition, whether the intestinal microbiota is affected by treatment with *Lactobacillus rhamnosus* and *Lactobacillus reuteri* and whether differences in the vaginal microbiome have an impact on the above

Method

Study design

[figure not shown]
The study program is designed as a prospective, double-blind, randomized case-cross over study. The study program last 6 months.

The women are randomized to the treatment group (capsule Femidur containing two types of lactobacilli) and to the control group (placebo capsule). After three months, the women cross, and the group that received treatment now receives a placebo and vice versa. The women remain blinded throughout the period for both themselves and the staff.

Randomizing

Randomization of the women takes place by extraction in the electronic system RedCap where the woman's grouping in the study is determined. The woman is anonymized in the study by linking her CPR number to a study number. The tests she submits during her studies are linked to this number. After randomization and submission of samples and questionnaire, the capsules (Femidur® or placebo) are dispensed.

Overview of project progress:

Study Setup and intervention

The included women are divided into two groups. Women in both groups fill out the drinking and water-diary (DWD) over 3 days as well as the ICIQ-OAB and ICIQ-UI-SF questionnaires. A freshly loaded urine sample, a vaginal swab from the top of the vagina and a stool sample are then delivered. The vaginal swab can be taken by the patient himself, or by the doctor/nurse. The urine sample is freshly loaded mid-stream urine. The stool sample can be taken at home and stored up to 7 days in a regular freezer.

The women are then given the capsules, which they take every day for 3 months.

After 1.5 months, all the women show up in the outpatient clinic where urine samples and vaginal swabs are made, and stool samples are delivered. The women fill out the ICIQ-OAB and ICIQ-UI-SF questionnaires.

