Some of the women will already be treated with topical estrogen initiated by their general practitioner. For those women who are already being treated with topical estrogen, this is continued. For the women with a wish to participate in the study, it is noted in the project papers whether the woman is taking estrogen and whether it is topical or systemic treatment. If the woman enters the trial and are not already undergoing estrogen therapy, a possible start-up is awaited until after the end of the trial.

At the inclusion data on height, weight, tobacco and alcohol consumption, drug status, parity, previous cancers, diseases, and operations in the abdomen as well as constipation is collected. Information from the journal of the women is not used for the study.

If the woman has rUTI, she is informed about the trial and offered written material as well as a call for further information.

Standards

Femidur® is produced by Pharmaforce, a Danish company founded in 2005. Femidur® capsules are made from gelatin from plants, as well as maltodextrin. Femidur® contains 2 vaginal lactic acid bacteria; Lactobacillus rhamnosus GR-1® and Lactobacillus reuteri RC-14®, both of which can colonize the vagina after oral ingestion. Femidur® contains 5 billion vaginal lactic acid bacteria per capsule of Femidur®. Femidur® capsules should be swallowed whole.

The women are given capsules Femidur® once. It is either at startup or after three months, dependent on the randomization.

The placebo capsules will match Femidur® in appearance. The placebo capsules consist primarily of gelatin from plants and maltodextrin.

The distribution of capsules is planned to avoid the case where the women have capsules with both placebo and Femidur at home at the same time and may mix the two.

Statistical considerations

Number of patients for inclusion

To our knowledge, no previous studies have been conducted on lactobacilli and their possible impact on the urinary microbiome. The number of women to be included to achieve a sufficient number in relation to strength calculation is therefore difficult to estimate. There are other studies available on the vaginal microbiome and disease, and based on these¹⁸, it is planned to include 100 women in total.

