Previous studies on postmenopausal women have shown a very small drop-out rate and a high inclusion rate¹⁹, which is why it is expected that the required number of women can be included within a limited period. The inclusion period will continue until the 100 women are included. If there are drop out during the first 3 months, a similar number to the drop out will be included until there is a total population of 100 women.

Statistical variables and data

Variables that are compared between the groups are operational taxonomic unit (OTU) richness (number of unique bacteria) and Shannon Index (the distribution of the bacteria in the sample) and expressions of alpha diversity. Beta diversity, which expresses how bacterial composition varies between samples, is assessed using PCA plots with Hellinger transformation or Principal Bray-Curtis. Heatmaps are used for further assessment of differences and similarities.

Numerical parametric data is given as mean +/- SD while non-parametric data is given as median and range. IBM SPSS Statistics 22 and R (the R foundation) will be used for statistical analysis. The data material will contain demographic data (age, smoking status, births, etc.) and the composition of the microbiome in the vagina, bladder and intestines will be used. Data that will undergo analysis is descriptive patient data, the urine-microbiome and its composition, vaginal and gut microbiome composition and results around rUTI. For all variables, p-values will be calculated and values <0.05 are significant.

Subjects

The women included in the study must be postmenopausal and with a minimum of 3 years of menostasis. If the women have undergone hysterectomy before menopause, the woman must be at least 60 years old when they are included. The women must be diagnosed with rUTI.

The diagnosis of rUTI is made by either:

- (a) Three cultivation-verified UTI in a year, or
- (b) Two cultivation-verified UTI over the course of six months.

If the woman is diagnosed with rUTI, a positive culture response will be checked before the woman arrive at the outpatient clinic. If there are no culture responses in the hospital's medical record system, contact is

[figure not shown]
Protocol

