Passing a urine and stool sample is not considered associated with pain. The very act of handing in a sample, especially with feces, can for some be associated with discomfort and modesty. The treatment staff acts professionally and tries to ease this situation for the patient. If it is a major burden on the patient, it is expected that the patient will not sign up for the trial. Performing vaginal swabs can be uncomfortable for some women but not painful or dangerous. The women can take the swab themselves or have it taken by a healthcare professional, which one is associated with the least discomfort for the women.

Clinical tests, sampling of biological material.

All clinical samples are collected at baseline, after 1.5, 3, 4.5 and 6 months.

Urine samples

At each visit, the women deliver a freshly voided urine sample in a sterile container, 50 ml each time. The women must have physical attendance when the urine sample is made, as this must be done in comparable rooms each time and be fresh. Urine is taken to normal culture at the department of clinical microbiology (10 ml) and 40 ml of the remaining urine is divided into four tubes and frozen to -80 degrees Celsius. There are two freezers, one is placed at the Department of Clinical Microbiology at Aalborg University Hospital, and the other at the North Jutland Regional Hospital. The frozen urine is stored until analysis. Urine is examined using 16s rRNA sequencing to identify bacterial DNA in the urine and thus describe bacterial types and distribution.

Vaginal swab

At each visit, all women deliver a vaginal swab that is placed in a sterile container. The inoculation is subject to the same conditions as urine, and it must therefore be made at the hospital every time. The container with vaginal swab is then stored in a freezer at the department of microbiology, Aalborg University Hospital or North Jutland Regional Hospital, at -80 degrees Celsius. The sample is examined using 16s rRNA sequencing to identify bacterial DNA in the vagina and thus describe the bacterial types and distribution.

Stool samples

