All biological material will be stored at the Centre for Clinical Research, North Jutland Regional Hospital for a maximum of 15 years. For all types of sample material, purified DNA is stored, and frozen original samples are stored – 10 ml of urine and vaginal samples. The samples will be stored in accordance with current guidelines and after approval from the Danish Data Protection Agency. Further studies on the samples in the biobank can only be carried out after new approval from the Scientific Ethics Committee and obtaining new consent from the included women. In the event that a new analysis of the samples will not result in a risk to the women, the Research Ethics Committee is applied for permission to analyze the samples without the consent of the included women. The biological material shall be stored for possible subsequent analysis of bacteria or fungi. None of the material is sent abroad.

Research ethics section

The project follows the ethical rules described in the Helsinki Declaration.

The project is initiated by Consultant [name] and Department Physician [name]

The project is considered a public research project and is notified via the region. Patient consent is obtained after oral and written information to the patient.

The purpose of the study is to look at the change of the urinary microbiome when influenced by lactobacilli and whether this has an impact on the prevention of rUTI. To ensure that the link being investigated is between lactobacilli and the urinary microbiome, samples of the gut and vagina's microbiome are also taken.

The study is set up as a cross-over study, so that all the women receive both placebo and active treatment. By presenting the study this way, the possible effect of lactobacilli on the urinary microbiome in women with rUTI could be found by comparing the urinary microbiome in the treatment group and the placebo group. By letting the groups cross treatment after three months, they become additional control group for

themselves. This is important as the urinary microbiome between individuals is very different, whereas in the same woman it is stable over time unless she gets a urinary tract infection.

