Protocol

The primary recruitment takes place when the patients are referred to gynecological outpatient clinics at either Aalborg University Hospital or Regional Hospital Nordjylland, Hjørring. Women referred with rUTI referred to the urology department in Frederikshavn can also be included.

The women may be referred with the problem rUTI, or the diagnosis is made in connection with the woman meeting in the outpatient clinic with other problems. If the woman has rUTI, she is offered to participate in the study in connection with her attendance at the outpatient clinic, and if she has an interest, the written patient material is provided. She is then contacted by the project manager and invited to a meeting and further information.

At the start of the study, contact will be made via the regional practice coordinator to the general practitioners to inform about the study. During the study, it will be possible to refer women with rUTI to gynecological outpatient clinics in Aalborg earlier than usual. In addition, the private gynecologists in the pre-hospital setting will be informed of the project and the opportunity of referring to it. It will be possible, in agreement with the private gynecologist, to provide small patient booklets with information on the study in the gynecological practice.

In the waiting rooms of the gynecological outpatient clinic, there will also be pamphlets with information material so that women who come for other reasons can be informed of the study. If this happens, the outpatient doctor will be able to refer the woman for rUTI examination to the uro-gynecological team in the usual way. After that, the woman will be included as previously described.

Two smaller papers and a more detailed description of the project have therefore been prepared for this purpose. The latter is only dispensing s if the patient meets the inclusion criteria and does not fall for the exclusion criteria.

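### Hospital is used neither in the allocation nor in the comparison between groups, which adds small, avoidable noise to comparisons between women, chiefly Femidur v placebo in months 0-3

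*Combined protocol and SAP*

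**What the plan says.** **Where women come from.** The Recruitment section names the gynaecological outpatient clinics in Aalborg and Hjørring as the main sources and adds a third: "Women referred with rUTI referred to the urology department in Frederikshavn can also be included". Faster access is described for one place only: "During the study, it will be possible to refer women with rUTI to gynecological outpatient clinics in Aalborg earlier than usual".

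**Where samples go.** Under Urine samples, frozen storage is split between two sites: "one is placed at the Department of Clinical Microbiology at Aalborg University Hospital, and the other at the North Jutland Regional Hospital". Both hospitals are named again in the vaginal swab and stool sections. Urine is to be taken in comparable rooms at each visit and swabs at the hospital, but no sentence says that a woman's five visits are at the same hospital.

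**Allocation.** Under Randomizing: "Randomization of the women takes place by extraction in the electronic system RedCap". No stratification factor is named.

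**Analysis.** Under Statistical variables and data: "Variables that are compared between the groups are operational taxonomic unit (OTU) richness". No model, paired test or hospital term follows. The Research ethics section expects to find the effect by "comparing the urinary microbiome in the treatment group and the placebo group", with each woman's own second period as an additional control. The background section, however, gives comparison of the same woman on placebo and on active treatment as the reason for the design.

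**Cross-over.** Under Study Setup and intervention, the second set of capsules is dispensed at the month 3 visit, and no washout is described.

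**The concern.** The plan itself gives reasons why women at different hospitals may differ. Earlier referral to Aalborg could bring women in sooner after their qualifying infections, and the plan says that a woman's urinary microbiome is stable unless she has a urinary tract infection. Frederikshavn adds women referred to urology instead of gynaecology.

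In a comparison between women, such differences add to the error variance and can fall unevenly on the two sequences by chance. The comparison most exposed is Femidur v placebo in months 0-3. It matters because, with no washout, it is the only treatment comparison that carry-over cannot affect, so a reader who doubts the second period will turn to it. It also has the least precision to spare: the plan gives no power calculation and says of the sample size that "The number of women to be included to achieve a sufficient number in relation to strength calculation is therefore difficult to estimate".

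**Working it through.** **Inputs from the documents.** Total sample size: "it is planned to include 100 women in total", with drop-outs in the first three months replaced. Two periods of three months. Significance at p < 0.05. The plan's 100 cannot be reproduced, because no effect size, SD, power or within-woman correlation is given.

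**Assumptions.** 50 women per sequence (the ratio is not stated). Two sampling hospitals with a split of 50/50, 60/40 or 70/30. A constant difference between hospitals of d = 0.3 to 0.8 SD, where SD is the between-women SD within a hospital at one visit. The documents give no figure for any of these.

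**1. How often the hospital shares differ.** Draw 50 of 100 women without stratification, with K of the 100 from one hospital. The number k of these in the first sequence is hypergeometric (100, K, 50), and the difference in share is k/50 − (K − k)/50.

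| Split | P(difference ≥ 10 points) | P(difference ≥ 20 points) | SD of difference |
|---|---|---|---|
| 50/50 | 0.32 | 0.07 | 0.10 |
| 60/40 | 0.31 | 0.07 | 0.10 |
| 70/30 | 0.28 | 0.05 | 0.09 |

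A typical imbalance is therefore about 10 points.

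**2. What that does to the month 0-3 comparison.** Shift in the estimate = imbalance × d. At 10 points: 0.10 × 0.3 = 0.03 SD to 0.10 × 0.8 = 0.08 SD. At 20 points: 0.06 to 0.16 SD. Standard error for 50 v 50 = √(2/50) = 0.20 SD.

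**3. The same effect as sample size.** With hospital share p, leaving hospital out multiplies the error variance, and so the required N, by 1 + p(1 − p)d². At 50/50: 1 + 0.25 × 0.09 = 1.02 for d = 0.3, and 1 + 0.25 × 0.64 = 1.16 for d = 0.8. At 70/30: 1 + 0.21 × 0.09 = 1.02 and 1 + 0.21 × 0.64 = 1.13. The cost is about 2-16% in N, for this comparison only.

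**4. The within-woman contrast.** If a woman stays at one hospital, the same hospital constant is in her active and her placebo value, and it subtracts out. The contribution is exactly 0. Only a difference between hospitals that changes from one period to the next would remain. Because the cross-over estimate is half the difference between sequences in the period differences, it would enter at half the size in step 2.

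**5. Simulation.** 100 women, 50 per sequence, two hospitals 50/50, between-woman and within-woman variance 0.5 each, true effect 0.3 SD (all assumed).

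| Analysis | Power at hospital shift 0 / 0.5 / 1.0 SD | Type I error |
|---|---|---|
| Within-woman cross-over | 0.84 / 0.85 / 0.83 | about 0.05 |
| First period only, between women | 0.32 / 0.31 / 0.27 | about 0.05 |
| All active v all placebo samples, unpaired | 0.58 / 0.56 / 0.45 | below 0.01 |

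In the third analysis with complete data, hospital imbalance is zero because each woman is on both sides. Hospital adds only noise there, and the larger loss comes from ignoring the pairing.

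**The case against.** The strongest reply is that this is a cross-over, chosen because women differ so much from each other, and that a fixed hospital effect vanishes in the comparison it was built for. No section defines a treatment comparison restricted to months 0-3. Leaving hospital out keeps the tests valid, chance imbalance is already covered by the standard error, and a shift of 0.03-0.08 SD is small beside 0.20 SD. On this view the more basic gap is that no within-woman, period-adjusted analysis is specified.

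All of that stands as a limit on the size of the point. It does not remove it, because the statistics and ethics sections describe a comparison of groups and treat the woman as her own control only in addition. The cancellation also relies on a same-hospital rule that the plan does not state. Comparable rooms at each visit is a useful control but not that rule.

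Three stronger readings are tempting, and the documents do not support them:

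- **Earlier referral to Aalborg biases the trial.** Referral comes before randomisation, so it affects both sequences alike in expectation. It changes case mix, and a current infection is treated before inclusion in any case.
- **There are three sampling sites.** Three places supply women. Only two hospitals store samples, and information meetings are held at one of two gynaecological departments.
- **The two hospitals handle samples differently.** Both freeze at −80 °C, and the plan describes one extraction method for urine, one for swabs, and one sequencing facility. No difference in handling is documented.

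**Conclusion.** The point holds as a cheap improvement with a small gain. Hospital is absent from both allocation and analysis, and this costs some precision in comparisons between women: about 2-16% in required sample size for hospital differences of 0.3-0.8 SD, with hospital shares 10 or more points apart in roughly three allocations in ten. It does not threaten the validity of any test, and for a woman who stays at one hospital it has no effect on the within-woman contrast.

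The size rests on assumed hospital splits, equal sequences and an assumed hospital difference. If the hospitals do not in fact differ, the loss is nil. A reader might infer that a hospital term would repair the analysis plan as a whole. It would not: the within-woman, period-adjusted analysis is still the main contrast, and the hospital term only supports the comparisons between women.

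**What to change.** - **Randomizing:** stratify the REDCap sequence allocation by sampling hospital (Aalborg; Regional Hospital Nordjylland), with blocks within each hospital.
- **Study Setup and intervention:** record the hospital, and have each woman give all five sets of samples at the same one, so that hospital cancels in the within-woman contrast. Assign women from Frederikshavn to one of the two sampling hospitals.
- **Statistical variables and data:** include hospital as a factor in any Femidur-placebo comparison between women, and permute within hospital for composition tests of that comparison. State that the within-woman, period-adjusted contrast is the main one.

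If recruitment has started, apply the same-hospital rule and the analysis part only.

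The cost is one REDCap setting, two or three sentences of text and one or two degrees of freedom. Women from Frederikshavn may have some extra travel, although they already attend one of the two gynaecological departments for the information meeting. No further patients or procedures are needed.
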